#### **E.6.a.2 Duration of Botox**

An intramuscular injection of Botox results in flaccid paralysis that gradually improves over an average of 2 to 4 months. Although the effects are temporary, paralyzing the primary plantar flexors in the lower leg could prove problematic and result in gait disturbances contributing to subsequent falls. For this reason, pilon fractures have been chosen for this study because it is an injury which not only commonly results in ankle stiffness, but it also requires a non-weight bearing status for approximately 3 months, allowing the botulinum toxin to run its course without interfering with return to normal function. The effects of Botox are entirely reversible over time, and long term effects are unlikely to be experienced.

**E.6.b Foreseeable Benefits:** The specific aims of this study are to provide improved outcomes of operatively treated tibial plafond fractures by using Botox to improve ankle dorsiflexion. Patients randomized to the Botox arm of the study have the potential to experience increased ankle dorsiflexion, which will result in improved gait and lower limb functionality, as well as reduce the risk of developing other lower extremity pathologies.

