Even after the initial spasms have subsided, Botox may aid in the prevention of contracture and help facilitate therapeutic stretching techniques by reducing the basal tone of the plantar flexors. Even at rest, muscles exert a baseline tone to maintain posture and joint position. By weakening or paralyzing the gastrocsoleus complex, there would be an imbalance in muscular tone in the lower leg pulling the foot into a more dorsiflexed position even at rest. This will also reduce voluntary and involuntary guarding during stretching exercises, thus improving the effectiveness of rehabilitation regimens.

**B.10 Summary:** Based on Botox's ability to reduce pain and postoperative muscular spasms while at the same time eliminating resting basal tone of the primary plantar flexors about the ankle, it is felt that intramuscular injections will be beneficial in aiding therapeutic stretching exercises which is essential for maintaining ankle range of motion. These exercises will be started approximately 2 weeks after the time of definitive fixation which is well within the 8-10 weeks of maximal effect seen with intramuscular botulinum toxin injections. Botulinum toxin injections have not only been shown to prevent the development in of contractures, but also used to treat contractures which have already formed. The purpose of this study is to evaluate the effect of Botulinum toxin A injections into the gastrocsoleus complex on ankle dorsiflexion after staged internal fixation of tibial plafond fractures. If Botulinum toxin A proves effective, this approach could have a significant impact on the practice and outcomes of orthopaedic surgery and will allow for treatment and prevention of equinus contracture without the morbidity associated with an additional surgical procedure.

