All patients will be treated by a fellowship trained orthopaedic surgeon who has completed advanced training in either trauma or foot and ankle surgery. Patients will all undergo a staged fixation approach which involves primary external fixation with irrigation and debridement if necessary, followed by open reduction and internal fixation when soft tissues allow. Additional procedures on the injured extremity that take place between external fixation and definitive fixation (ex: ORIF of the fibula or repeat irrigation and debridement) do not disqualify the patient from the study as long as definitive fixation takes place within 3 weeks (21 days) of the injury. All definitive operations will take place at either Carolinas Medical Center – Main, or Carolinas Medical Center – Mercy.

At the time of definitive fixation, the hospital's investigational pharmacy will provide a blinded solution of either Botulinum toxin A or 0.9% sodium chloride solution for injection intraoperatively following skin closure. Four syringes containing 0.5 ml 0.9% sodium chloride, with or without Botulinum toxin type A based on the patient's randomization, will be provided and refrigerated until they are ready to be administered. Both the physician and the patient will be blinded to the contents of the syringe. Once reconstituted, botulinum toxin type A will only last for 4 hours at room temperature so it will be necessary to not allow the solution to sit at room temperature for an extended period of time. All patients in the study group will receive onabotulinumtoxinA, Botox® (Allergan, Irvine, California) provided by the investigational pharmacy. The total dose of botulinum toxin will be calculated based on the patient's weight in kilograms, such that a total dose of 200U of Botox will be used for a 70 kg individual (see Table 1 below). The dosage will scale linearly in

proportion to the patient's body weight, such that each kilogram change results in a 3U change in Botox (rounded to the nearest 30U interval change from 200U, with a maximum of 300U). This dosing regimen was chosen based on the effective dose for an average gastrocnemius from other studies.

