**Table 1: Botox Dosing by Weight**

45-55 kg:	140 U
55-65 kg:	170 U
65-75 kg:	200 U
75-85 kg:	230 U
85-95 kg:	260 U
95-105 kg:	290 U
105-115 kg:	300 U

At the completion of surgery, the gastrocsoleus complex will be injected in four locations (superior medial, superior lateral, inferior medial, and inferior lateral) prior to the application of short leg splint, per the recommendation of prior studies. At each injection site,  $\frac{1}{4}$  of the total dose of botulinum toxin A or normal saline will administered in approximately 0.5 ml injections. The use of EMG or other imaging modalities has been recommended to ensure accuracy of botulinum toxin injection at the target muscle motor end plates, however it is not necessary when injecting the gastrocsoleus complex, even in small children due to its large size and superficial location. The injection sites are illustrated in the figure 2 below:

[figure not shown]

Figure 2

Following definitive fixation and study injections, patients will be placed in a well-padded splint in at least neutral dorsiflexion for two weeks to allow for wound healing. Following wound healing, patients will transition to a removable orthosis and begin range of motion exercises and stretching techniques. All patients will undergo a structured exercise regimen. Each patient will receive a pamphlet at an 8th grade reading level containing a standardized exercise protocol which clearly states the exercises to be utilized, the frequency, and duration. As long as there are no adverse events, patients will proceed to touch down weight bearing at roughly 6 weeks postoperatively and continue their exercise program. Patients will then advance to partial weight bearing at approximately eight weeks and full weight bearing as tolerated at 10 to 12 weeks, as long as no adverse events occur precluding this progression.

Study participants will return to regularly scheduled follow-up appointments to monitor their progress. At each follow-up appointment (2 weeks, 6 weeks, 12 weeks, 6 months, and 1 year), patients will be monitored for signs and symptoms of Botox toxicity. All patients will be seen in follow-up at one of two clinic locations. At each site, research staff familiar with the study will be present along with a device for measuring dorsiflexion in a standardized fashion.

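### The fall-risk argument relies on about 3 months of non-weight bearing, but partial loading is scheduled about 8 weeks after injection, and falls are not a named safety item

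*Combined protocol and SAP*

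**What the plan says.** All references are to the combined protocol and SAP.

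- **Hazard and answer (E.6.a.2).** Paralysing the plantar flexors could "result in gait disturbances contributing to subsequent falls". The section says pilon fractures were chosen because the injury often leads to stiffness and also "requires a non-weight bearing status for approximately 3 months, allowing the botulinum toxin to run its course".
- **Duration of effect.** E.6.a.2 says an injection "results in flaccid paralysis that gradually improves over an average of 2 to 4 months". B.10 says that exercises beginning about 2 weeks after fixation fall "well within the 8-10 weeks of maximal effect seen with intramuscular botulinum toxin injections".
- **Time of injection (D.3).** The syringes are supplied "for injection intraoperatively following skin closure" at the definitive operation, so postoperative weeks are also weeks since injection. Patients remain eligible "as long as definitive fixation takes place within 3 weeks (21 days) of the injury". D.7 expects roughly 14 days between injury and fixation.
- **Loading schedule (D.3, after Table 1).** If there are no adverse events, "patients will proceed to touch down weight bearing at roughly 6 weeks postoperatively". They then "advance to partial weight bearing at approximately eight weeks and full weight bearing as tolerated at 10 to 12 weeks", again subject to adverse events.
- **Safety capture.** D.3 provides for toxicity checks at every visit (2, 6 and 12 weeks, 6 months, 1 year). The D.2 complications list includes rehospitalizations and additional surgeries but not falls. E.7 restricts the adverse events considered to those beyond what one would expect in a post-operative trauma patient. It requires the treating physician to tell the safety monitor within 24 hours.

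**The concern.** E.6.a.2 is the protocol's argument for why temporary calf paralysis is acceptable in this population: patients will not be walking on the limb while the toxin acts. The D.3 schedule has them loading it earlier than that. The stated protection is therefore not the one that the schedule delivers.

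This also bears on data capture. Falls are the hazard that the protocol itself names, yet whether a fall is recorded depends on whether each clinician sees it as a sign of toxicity, as an expected event after trauma surgery, or as neither. This pilot is meant to test procedures and inform a full trial, and its data may be pooled with that trial (D.8). It could end without a consistent fall count in either arm, and the monitor's comparison of arms would then lack that input.

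**Working it through.** **Inputs.** From D.3: touch-down at week 6, partial loading at week 8 and full loading at weeks 10 to 12, all read as weeks after surgery and so after injection. From E.6.a.2: 3 months of non-weight bearing, and average recovery over 2 to 4 months. From B.10: 8-10 weeks of maximal effect. Injury to fixation: 14 days (D.7), at most 21 (D.3).

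**Conversion.** One month = 365.25/12/7 = 4.348 weeks, so 2, 3, 4 and 6 months are 8.7, 13.0, 17.4 and 26.1 weeks.

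**Step 1. Where the 3-month figure fits.** Full loading counted from injury:
- 14 days to fixation: 10 + 2 = 12 to 12 + 2 = 14 weeks
- 21 days to fixation: 10 + 3 = 13 to 12 + 3 = 15 weeks

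Both ranges agree with about 13.0 weeks. The figure is reproduced as the time from injury to full loading.

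**Step 2. The figure as a non-weight-bearing period.** Gap between partial loading and 3 months:
- from injection: 13.0 - 8 = 5.0 weeks
- from injury, 14 days: 13.0 - (8 + 2) = 3.0 weeks
- from injury, 21 days: 13.0 - (8 + 3) = 2.0 weeks

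Touch-down, which is minimal load, comes 13.0 - 6 = 7.0 weeks before 3 months from injection. For wear-off, only time since injection counts. The 2 to 3 weeks before fixation pass before any toxin has been given.

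**Step 3. Against maximal effect.** I take the 8-10 weeks to run from injection, because B.10 places week 2 within them.
- Partial loading begins 8 - 8 = 0 to 10 - 8 = 2.0 weeks before the end.
- Full loading begins 10 - 10 = 0 to 12 - 8 = 4.0 weeks after the end.

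If the phrase instead meant a window from week 8 to week 10, partial loading would coincide with its start.

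**Step 4. Against the 2 to 4 month recovery range (8.7 to 17.4 weeks).**
- Partial loading: 8.7 - 8 = 0.7 weeks before the lower end (negligible, since both figures are approximate), and 17.4 - 8 = 9.4 weeks before the upper end.
- Full loading: 10 - 8.7 = 1.3 to 12 - 8.7 = 3.3 weeks after the lower end, and 17.4 - 12 = 5.4 to 17.4 - 10 = 7.4 weeks before the upper end.

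These are calendar gaps, not weeks of full paralysis, because recovery is gradual.

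**Step 5. Which visits cover the period of interest.** This runs from partial loading (week 8) to the upper end of the recovery range (week 17.4).
- A question at 12 weeks about falls since the 6-week visit covers 12 - 6 = 6 weeks. It takes in all partial loading before full loading begins, and the first 12 - 12 = 0 to 12 - 10 = 2 weeks of full loading.
- A question at 6 months covers 26.1 - 12 = 14.1 weeks, including the remaining 17.4 - 12 = 5.4 weeks of the period.

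Together the two visits span weeks 6 to 26.1.

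**The case against.** The strongest reply is that E.6.a.2 uses non-weight bearing loosely for not yet fully weight bearing. Counted from injury, that agrees with D.3, and full loading does not overlap maximal effect. What remains is partial loading 0 to 2.0 weeks before maximal effect ends, on a schedule stated only approximately. This is a fair account of how the sentence may have arisen. It does not restore the safety argument, because the toxin starts at fixation and full loading still begins before the upper end of the recovery range.

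A reader might go further and infer that the 3-month figure cannot be reconciled with D.3 from any starting point. That is too firm. With 21 days to fixation the gap from injury is 2.0 weeks, and both figures are approximate.

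The duration data are also soft. The 2 to 4 months is a range of averages, not a recovery endpoint. The 8-10 weeks comes from a cited source not available here.

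Safeguards exist. Progression depends on there being no adverse events, full loading is as tolerated, patients move to a removable orthosis after wound healing, and time to full loading and weight-bearing compliance are recorded. They limit the concern but do not close it: no visit is listed at week 8 or 10, no calf-strength check is named, and the physician is blinded to the injection.

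A reader might also infer that fall data will be lost. The documents show only that they could be. The examples that E.7 gives of side effects common at baseline include generalized weakness but not falls. The D.3 toxicity checks may pick up some falls, and rehospitalization or additional surgery some injurious ones.

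**Conclusion.** The concern holds as a mismatch between the stated protection and the schedule, together with a gap in what is recorded. Partial loading begins about 5 weeks before 3 months from injection, at or within the stated period of maximal effect. Full loading begins inside the stated average recovery range, 5.4 to 7.4 weeks before its upper end. This assumes that the D.3 weeks count from the operation at which the toxin is given and that maximal effect counts from injection. The mismatch is certain from the text; incomplete recording of falls is possible rather than established.

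It might be inferred that treated patients will fall more often, or that the loading schedule is unsafe and should be delayed. The documents support neither. Recovery is gradual, and how many patients will still be weak when they load the limb is unknown. No excess of falls is claimed and no change to the loading schedule is asked for. The point merits correction because the hazard is the protocol's own and the remedy is small.

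**What to change.** 1. **E.6.a.2.** Replace the 3-month statement with the D.3 schedule: touch-down at about 6 weeks after injection, partial loading at about 8, full loading as tolerated at 10 to 12. Add that calf weakness may persist when loading begins and that progression depends on there being no adverse events.
2. **D.2 complications list.** Add falls since the last visit (number, approximate date, injury yes/no), asked in both arms at least at the 12-week and 6-month visits. Asking at all five visits is optional: the 1-year answer lies beyond the period of interest and would need about 26 weeks of recall.
3. **E.7.** State that falls go to the safety monitor as counts by arm, are exempt from the filter for expected events, and that injurious falls are notified within the existing 24 hours.
4. **Analysis.** Tabulate by arm, descriptively and without a test: patients with at least one fall, and number of falls. D.3 allows a bilateral patient to have one limb in each arm; list such a patient separately, because a fall cannot be assigned to one arm.

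**Cost.** One wording correction, one or two sentences in E.7, and one form item: 20 patients x 2 visits = at most 40 entries. No visits or patients are added. The downside is recall: the 6-month answer looks back about 14 weeks, so dates will be approximate.

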### **A. Specific Aims**

Tibial plafond fractures account for 7-10% of all tibia fractures and are potentially devastating injuries that continue to provide treatment challenges for orthopaedic traumatologists. While most trauma centers have adopted a staged protocol with initial external fixation followed by delayed internal fixation after soft tissue recovery, patients continue to report relatively poor physical and psychosocial outcomes. A significant reduction in range of motion is commonly observed after operative fixation of tibial plafond fractures, specifically loss of dorsiflexion. If the decrease in dorsiflexion is severe enough, it is termed equinus contracture and can pose functional limitations and contribute to additional lower limb pathologies in those suffering from it. Botulinum toxin A has been shown to be effective in increasing dorsiflexion in children with equinus contracture from muscle spasticity from cerebral palsy. More recently, promising results have been seen in using Botulinum toxin A in the treatment of contractures following Achilles tendon repair and total knee arthroplasty. The purpose of this study is to evaluate the effect of Botulinum toxin A injections into the gastrocsoleus complex on ankle dorsiflexion following internal fixation of tibial plafond fractures.

Specific Aim 1: To determine if the use of Botulinum toxin A intramuscular injections of the gastrocsoleus complex in patients with operatively treated tibial plafond fractures will result in increased ankle dorsiflexion when compared to controls.

Hypothesis 1: The group treated with Botulinum toxin A injections will have increased ankle dorsiflexion when compared to controls at 6 and 12 months.

Specific Aim 2: To determine if the use of Botulinum toxin A injections in patients with operatively treated tibial plafond fractures will lead to increased ankle functionality as measured by the FAAM, and quality of life as measured by the SF-36, when compared to controls.

Hypothesis 2: The group treated with Botulinum toxin A injections will report more positive health-related quality of life when compared to controls at 6 and 12 months.

Specific Aim 3: To determine if the use of Botulinum toxin A injections in patients with operatively treated tibial plafond fractures will lead to a higher proportion of patients achieving at least 10 degrees of dorsiflexion when compared to controls.

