Recent studies following outcomes on tibial plafond fractures have repeatedly shown dorsiflexion to be impacted. Grose and colleagues found the average dorsiflexion in their cohort to be 9 degrees with only 25% achieving greater than 10 degrees of dorsiflexion. Patients treated by Patterson and Cole achieved only 7 degrees of dorsiflexion after staged internal fixation. Marsh et al. measured an average dorsiflexion of 10 degrees with 50% of patients failing to reach at least 10 degrees of dorsiflexion, even after excluding those who underwent amputation or arthrodesis. Functional limitations such as difficulty climbing up stairs, walking up hills, and squatting to pick up objects are commonly reported problems following this injury, all of which reflect a loss of dorsiflexion. Clearly, stiffness is a ubiquitous problem in this population and carries with it the sequela of impaired functionality while contributing to other lower extremity problems.

**B.4 Treatment Options for Limited Range of Ankle Motion:** Once acquired, equinus contractures can be very difficult to treat. Physiotherapy and stretching are the first line therapy to improve this condition, but often only play a limited role in the correction of this condition. Surgical options remain the mainstay treatment for contractures that are causing significant functional impairment. Achilles tendon lengthening is one surgical option that addresses equinus contracture by lengthening the Achilles tendon by utilizing a Z-lengthening technique. This procedure has a long recovery time and carries with it the risk of skin slough, Achilles tendon rupture, and discomfort with shoewear. Because the Achilles tendon accounts only for 3-5% of the contracture, there is also concern that lengthening the tendon reduces its moment-generating capacity due to the gastrocsoleus' new position on the sarcomere length-strength curve, resulting in weakness in plantarflexion. Additionally, this procedure also carries with it the risk of over lengthening causing a profound loss of strength and resulting in a heel gait pattern.

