Other surgical options, such as the gastrocnemius recession, have been gaining popularity as an alternative to Achilles tendon lengthening in the treatment of equinus contractures, because it is able to address the contracture without resulting in loss of strength. One such technique, termed the Strayer recession, is performed by separating the gastrocnemius from the soleus and transecting it just proximal to the gastrocnemius-soleus aponeurosis. This allows the gastrocnemius muscle to retract proximally providing increased dorsiflexion. This procedure produces excellent results by achieving an average increase in dorsiflexion of 14-18 degrees, but it is not without complications. Sural neuropathy is a common complication of this procedure, either due to excessive retraction on the nerve at the time of surgery or proximal and distal tethering of the nerve within the gastrocsoleus complex during the release. Even though 42.5% of sural nerves run superficial to the fascia effectively protecting them from laceration during the release, sural and saphenous nerve lacerations can and do occur. Finally a significant number of patients report dissatisfaction with the scar left from the surgery which can pucker due to soft tissue adhesions, and exacerbated by retraction of the gastrocnemius muscle belly. Equinus contractures acquired after tibial plafond fractures are so problematic that some centers have advocated for performing a Strayer recession prophylactically at the time of fixation to prevent the development of such contractures.

**B.5 Botulinum Neurotoxin:** Botulinum toxin A (Botox) is an extremely potent neurotoxin produced by the bacterium *Clostridium botulinum* that results in transient flaccid muscle paralysis. To date, Botulinum toxin A and B are approved for use by the U.S. Food and Drug Administration for treatment of (1) chronic migraine headaches, (2) upper limb spasticity, (3) cervical dystonia, (4) strabismus and blepharospasm, (5) severe primary axillary hyperhidrosis, (6) and moderate to severe glabellar lines. In the orthopaedic literature, multiple potential indications have been identified including shoulder dislocations, adhesive capsulitis, talipes equinovarus, plantar fasciitis, torticollis, knee flexion contractures, lateral epicondylitis and cerebral palsy; all of which are currently considered "off-label."

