## **D.2 Outcome Variables**

### ***Primary Outcome Variable (objective):***

Ankle Dorsiflexion of Injured Extremity. The primary outcome variable will be ankle dorsiflexion of the injured extremity as measured by a goniometer and radiographs.

Ankle Dorsiflexion of Uninjured Extremity. In patients with a unilateral lower extremity injury, the ankle dorsiflexion of the uninjured extremity will be measured in the same fashion as the injured extremity.

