### ***Secondary Outcome Variables (self-report):***

The Short-Form 36 (SF-36) will be used to measure health related quality of life. The SF-36 is a commonly used general health status measure and assessment of function, which allows individuals to describe their own health status. It allows for the comparison between individuals with the same condition as well as to the general population. Subscale scores measure various domains of health and quality of life, while the physical (PCS) and mental (MCS) component summary scores represent the main dimensions of health. The PCS and MCS scores range from 0 to 100 points and are standardized to population norms with higher scores indicating higher function. The mean score for the PCS and MCS in the general population is 50 points with 10 points representing one standard deviation from the mean.

Pain. Overall Study limb as well as ankle specific pain intensity will be measured using the 0-10 visual analogue scale used in the Brief Pain Inventory. Pain intensity will be measured both at rest and during ambulation. The Brief Pain Inventory (BPI) will be administered to patients at 6 and 12-month follow-up appointments. The BPI is a widely used, 15-item measure of pain intensity and interference with daily life. The questionnaire assesses three key pain domains: pain intensity, pain interference, and efficacy of pain treatments or medications.

The Foot and Ankle Ability Measure (FAAM) is a well validated instrument that consists of 29 items measuring 2 broad categories: activities of daily living (84 points) and sports (32 points). The scores are normalized to 100 for each category and are reported separately. The FAAM will be obtained at 6 and 12 months to assess the functional status of the affected ankle.

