### ***Covariates***

#### ***Demographics***

- Age
- Race/ethnicity
- Gender
- BMI

- Co-morbidities
- Fracture classification
- Time until definitive fixation
- Tobacco use
- Workers compensation status
- Level of education
- Marital status
- Personal income
- Health insurance
- Working status before injury

These data will be abstracted from the medical record by the research staff.

*Additional Outcomes*

- Time until full weight bearing
- Time until return to work
- Compliance with weight bearing status
- Compliance with prescribed treatment

These data will be patient reported

*Complications*

- Nonunion
- Malunion
- Infection: Deep
- Infection: Superficial
- Osteomyelitis
- Wound breakdown
- Skin slough: partial thickness
- Skin slough: full thickness
- Additional surgeries: Strayer recession, Achilles lengthening, hardware removal, amputation, or arthrodesis.
- Rehospitalizations

These data will be captured during clinical exam at each office visit

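### No direct measure of calf strength is planned, so recovery of the injected muscle cannot be verified and a lasting deficit would show only indirectly

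*Combined protocol and SAP*

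**What the plan says.** **Outcomes.** D.2 states: "The primary outcome variable will be ankle dorsiflexion of the injured extremity as measured by a goniometer and radiographs". The secondary outcomes are questionnaires: SF-36, pain and the Brief Pain Inventory, and FAAM. On the last, D.2 says "The FAAM will be obtained at 6 and 12 months to assess the functional status of the affected ankle". Specific Aim 2 compares the arms on "increased ankle functionality as measured by the FAAM, and quality of life as measured by the SF-36, when compared to controls". Patient-reported additional outcomes include time to full weight bearing and time to return to work.

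**Complications.** The D.2 list covers union, infection, wound and skin problems, further surgery and rehospitalization. It adds: "These data will be captured during clinical exam at each office visit".

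**Strength in the background.** B.4 counts against Achilles lengthening the risk of "resulting in weakness in plantarflexion". It credits gastrocnemius recession with being "able to address the contracture without resulting in loss of strength".

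**Claims about the toxin.** E.6.a says all effects reverse given time, and E.6.a.2 repeats it: "The effects of Botox are entirely reversible over time, and long term effects are unlikely to be experienced". The Botulinum Toxin Safety section welcomes spread into the soleus and expects the extra weakness to add no functional impairment. E.6.a.2 nevertheless accepts that paralysing the plantar flexors could disturb gait and lead to falls.

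**Safety monitoring.** D.3 plans checks for toxicity at 2, 6 and 12 weeks, 6 months and 1 year, without defining their content. E.7 considers only events beyond those expected after trauma surgery, and gives generalized weakness as an example of a complaint common at baseline in this population.

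**The concern.** The intervention works by weakening a muscle, and the protocol judges rival treatments by whether they weaken that same muscle. It does not apply that test to its own treatment. If some weakness remained at 6 or 12 months, dorsiflexion could still look better, and nothing in the data would show directly what had happened to the calf.

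The pilot also feeds later decisions. D.5 uses it to decide whether results are clearly inferior, in which case the full trial is not run. D.5 and D.8 use it to plan the full trial and to contribute patients to it. D.8 makes that pooling conditional on an unchanged protocol. A strength measure added only after the pilot would put pooling in question and leave the first 20 patients without it.

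**Working it through.** The plan gives no figure on this point to reproduce: no power calculation, SD or margin. The check is therefore a reading of the outcome lists, followed by the precision an added measure would have.

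**1. Where could calf strength be recorded?**
- D.2 primary outcome: dorsiflexion, with the uninjured side as comparison in unilateral cases. No strength or plantarflexion range.
- D.2 secondary outcomes: self-report only.
- D.2 covariates and additional outcomes: none on strength. Time to full weight bearing and return to work are indirect.
- D.2 complications: no weakness, gait disturbance or falls. Rehospitalization would catch only events that lead to admission.
- D.3 clinical assessment: a physical exam of unstated content, plus questionnaires. No strength test or heel-rise is named.

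Direct measures found: none.

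**2. Would safety reporting fill the gap?** The D.3 toxicity checks have no defined content. E.7 sets aside expected post-operative complaints and names generalized weakness as common at baseline. It does not name calf weakness, so whether that counts is left to judgement. The two visit lists differ: D.3 runs to 1 year, while E.7 stops at 6 months.

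**3. Does the stated safeguard against falls match the schedule?** E.6.a.2 puts paralysis at an average of 2 to 4 months (2 × 52/12 = 8.7 weeks to 4 × 52/12 = 17.3 weeks). It relies on about 3 months (13 weeks) of non-weight bearing for the effect to pass. D.3 starts touch-down at about 6 weeks, partial loading at about 8 weeks and full loading at 10 to 12 weeks. All three steps come before 13 weeks. These passages disagree; no view is taken here on which is right.

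**4. What would an added strength measure show?** Inputs: 10 per arm (Specific Aims and D.2), significance level 0.05 (D.3, two-sided assumed), equal SDs. The documents give no strength SD, so results are in SD units. Eight per arm is an assumed level of follow-up.
- 95% half-width = t(0.975, 2n−2) × √(2/n)
- n = 10: 2.101 × 0.447 = 0.94 SD
- n = 8: 2.145 × 0.500 = 1.07 SD
- Difference detectable with 80% power, normal approximation, n = 10: (1.960 + 0.842) × 0.447 = 1.25 SD. With the noncentral t it is 1.32 SD (1.51 SD at n = 8).
- Power for a true deficit of 0.5 SD at n = 10, noncentral t: 18%
- Patients per arm to exclude a deficit of 0.5 SD (one-sided 0.025, 80% power, true difference zero; the margin is an assumption): 2 × (1.960 + 0.842)² / 0.5² = 62.8, so 63. For margins of 0.8 and 1.0 SD the numbers are 25 and 16.

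The pilot could therefore describe strength by arm and supply an SD for planning. It could not establish recovery.

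**The case against.** The strongest reply is that the plan does measure what patients would lose. FAAM daily-living and sports scores, SF-36, pain at rest and during walking, time to full weight bearing and return to work are all available for randomized comparison. They would reflect the net of motion gained and strength lost. This stands. A reader might infer that the trial cannot show net benefit or ignores the cost of paralysis; the documents do not support that. What chiefly limits a conclusion on net benefit is the sample of 20, which Specific Aims already concedes. What these measures cannot do is separate weakness from pain and stiffness, or show that the muscle has recovered.

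Second, reversibility is a statement about risk, not a hypothesis. A reader might infer that the trial sets out to test it, but none of the three hypotheses mentions it. Likewise B.10 says only that the approach, if effective, would act "without the morbidity associated with an additional surgical procedure". In B.4 that morbidity also includes skin, nerve and scar problems, so B.10 is not a promise of preserved strength.

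Third, lasting weakness is not shown in any source the protocol describes. The paralysis is said to ease before the 6-month visit, and B.6 reports no adverse events in 8 Achilles-repair patients followed for 2 years. That makes the harm uncertain. However, C and D.5 state that the investigators have no preliminary data for this use in this fracture.

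A reader might also extend the point to venous thrombosis. The documents do not mention it, and D.3 splints for only two weeks before a removable orthosis and exercises, so it has no basis here.

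**Conclusion.** The point holds in a limited form. No plantarflexion strength, heel-rise or plantarflexion range measure is specified, so recovery of the injected muscle cannot be verified. A lasting deficit would be visible only through general function and recovery measures. The E.7 filter may leave weakness uncounted as an adverse event. It is a gap in safety assessment and in planning data, and does not invalidate the planned comparisons.

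The added measure would itself be imprecise: about ±0.94 SD at 10 per arm, assuming complete data, independent patients and equal SDs, and about ±1.07 SD at 8 per arm. A null result would not show that strength had returned. The case for it rests on the pilot's stated purpose of testing procedures and informing the full trial.

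**What to change.** - **Add to D.2**, at the existing 6- and 12-month exams, a plantarflexion strength or heel-rise measure and plantarflexion range on the injured leg, taken by an assessor blinded to arm. Make side-to-side comparisons only in the D.3 subset with an uninjured opposite leg.
- **Set in advance a score for patients who cannot do the test**, so that the weakest are not lost as missing.
- **Report by arm with 95% intervals**, beside dorsiflexion, as descriptive pilot data and not as evidence of reversibility.
- **Record calf weakness and falls by arm at every visit**, whatever the E.7 filter decides.
- **Reconcile** E.6.a.2 with D.3 on weight bearing, and D.3 with E.7 on the safety visits.

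Cost: a protocol amendment, an extra case-report page and a few minutes per exam. The main downside is that some patients will be unable to do the test. Making the change before the pilot data are collected lets all 20 patients contribute.
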